We will randomize 20 PD patients to receive TZ or placebo. Ten of the participants will be randomized to receive TZ 5mg daily for 12 weeks and 10 participants will be randomized to receive a daily placebo for 12 weeks. This aim will generate data on safety and tolerability of TZ in a population of patients with PD. As an exploratory outcome, we aim to determine if treatment with TZ in patients with PD improves markers of energy metabolism. Furthermore, we will determine if cellular and cerebral ATP levels correlate with disease severity and progression. Participants will also participate in an assessment that will include, but is not limited to a motor exam, a neuropsychological assessment, and functional assessments. Clinical findings will be used to guide future clinical trials.

Interventions and Duration

Participants in this study will be randomized to receive either TZ 5 mg by mouth once daily or a matched placebo once daily. Once randomized, each participant will receive their assigned treatment for 12 weeks. Participants will be assessed via telephone for 3 weeks after their 2 week visit, then 6 weeks months after their baseline visit, then via telephone 9 weeks after their baseline visit, and their last visit will occur 12 weeks from their baseline visit. We anticipate that this study can be completed (study open to end of data analyses) within 9 months.

Sample Size and Population

This study will randomize 20 participants: 10 participants will be randomized to receive 5mg of TZ daily and 10 participants will be randomized to the placebo group. It is anticipated that no more than 35 participants will need to be screened to enroll these participants.

This study will include participants who are ≥ 40 years old who have a confirmed diagnosis of PD made by a neurologist and a Hoehn & Yahr score at baseline of < 4 . Participants will be excluded from this study if any of the following are true:

- Participants has orthostatic hypotension or a sitting blood pressure of $\leq 90/60$
- Participant is pregnant
- Participant has a deep brain stimulation device implanted
- Participant has a known allergy or sensitivity to terazosin
- Participant is concomitantly taking doxazosin, alfuzosin, prazosin, urapadil, or tamsulosin
- Participant has active drug or alcohol use or dependence that, in the opinion of the site investigator, would interfere with adherence to study requirements
- Participant is unable or unwilling to give written informed consent

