4.2 Exclusion Criteria

1. Subjects unwilling or unable to give informed consent
2. Secondary parkinsonism (e.g., drug induced)
3. Parkinson-plus syndromes
4. History of brain surgery for PD such as deep brain stimulation
5. No confounding acute or unstable medical, psychiatric, orthopedic condition. Subjects who have hypertension, diabetes mellitus, depression, or other common age-related

FAST TZ-PD

Version 1.8

Version date: 2/7/2019

illness will be included if their disease under control with stable treatment regimen for at least 30 days.

6. Neurogenic orthostatic hypotension defined as symptomatic decrease in BP > 20mmHg systolic or > 10mmHg diastolic and HR increase < 20bpm on supine to sitting or standing.
7. Clinically significant traumatic brain injury or post-traumatic stress disorder
8. Presence of other known medical or psychiatric comorbidity that in the investigator's opinion would compromise participation in the study
9. Presence of dementia per Movement Disorder Society Level I criteria
10. Major depression, bipolar affective disorder, or other mental health disorders that are sufficiently severe to increase adverse event risk or impact neuropathy assessment in the opinion of the responsible site principal investigator.
11. Current suicidal ideation within one year prior to the baseline visit as evidenced by answering "yes" to Questions 4 or 5 on the suicidal ideation portion of the Columbia-Suicide Severity Rating Scale (C-SSRS), Beck Depression score >21, Beck Anxiety score >22.
12. History of exposure to typical or atypical antipsychotics or other dopamine blocking agents within 6 months prior to the baseline visit
13. Use of investigational drugs within 30 days before screening
14. Subjects have to be on a stable regimen of central nervous system acting medications (benzodiazepines, antidepressants, hypnotics) for 30 days prior to the baseline visit
15. Use of doxazosin, alfuzosin, prazosin, or tamsulosin
16. For female participant, pregnancy, or plans for child-bearing during study period
17. Participant is restricted from traveling to and from the study site

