4.5.4 Randomization/Treatment Assignment

Participants will be randomized in a 1:1 fashion to TZ 5mg daily and placebo. Randomization will be performed by NuCara Pharmacy in Coralville, Iowa. Randomization codes will be made available only to the dispensing pharmacist. The randomization code will not be made available to the investigators, study centers, study subjects, or other representatives. Only after the study is complete, will randomization codes be made available to the investigators.

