6.3.12 Questionnaires

- MDS-UPDRS Part 1
 - This will measure Non-motor experiences of daily living
- MDS-UPDRS Part 2
 - This will measure Motor experiences of daily living
- The following cognitive assessments will be performed
 - Hopkins Verbal Learning Test (HVLT)
 - Symbol Digit Modalities Test (SDMT)
 - Montreal Cognitive Assessment (MoCA)
- Pittsburgh Sleep Quality Index
 - Assessment of sleep quality
- The following behavioral assessments will be performed to test depression, compulsiveness & anxiety
 - Beck Depression Inventory (BDI)
 - Beck Anxiety Inventory (BAI)
 - Columbia Suicide Severity Rating Scale (C-SSRS)
 - Parkinson's Disease Questionnaire (PDQ-39)

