9.2 Sample Size and Accrual

This is a pilot study and the sample size was chosen based on available funding and resources

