9.4 Data Analyses

The following outcome measures will be analyzed under an intention-to-treat protocol. All randomized individuals will be included regardless of their final treatment status.

- Primary Outcome
 - Rate of drop out between groups
 - Chi-square
 - Rate of adverse events between groups
 - Chi-square
- Secondary outcomes
 - Prevalence of orthostatic hypotension between placebo and active group
 - Chi-square
 - Prevalence of falls between placebo and active group
 - Chi-square
 - Differences in overall compliance between placebo and active group
 - Linear mixed effect models that includes compliance at each study visit for each participant
- Exploratory outcomes
 - Difference in ATP levels in red blood cells and brain within subjects before and after taking study drug on day 1
 - Paired samples t-test
 - Difference in ATP levels in red blood cells and brain within subjects at 6 and 12 weeks compared to baseline reading

- Paired samples t-test
- Difference in ATP levels in red blood cells and brain between groups at 6 weeks and 12 weeks
 - Independent samples t-test
- Slope of change over 12 weeks of the MDS-UPDRS Part 1
 - LMER
- Slope of change over 12 weeks of the MDS-UPDRS Part 2
 - LMER
- Slope of change over 12 weeks of the MDS-UPDRS Part 3
 - LMER
- Slope of change over 12 weeks of the MDS-UPDRS Part 4
 - LMER
- Absolute change over 12 weeks of the MDS-UPDRS Parts 1, 2, 3, 4, and TMS
 - Independent samples t-tests
- Slope of change over 12 weeks of MDS-UPDRS TMS (direct comparison for efficacy)
 - LMER
- Slope of change over 12 weeks of the Hoehn & Yahr Score
 - LMER
- Slope of change over 12 weeks of all cognitive assessments between placebo and active group
 - LMER
- Slope of change over 12 weeks of sleep assessments between placebo and active group
 - LMER
- Slope of change over 12 weeks of behavioral assessments between placebo and active group
 - LMER

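### The C-SSRS is planned only as a mixed-model slope and kept out of adverse events, so an emergent case may go unreported by arm; add a descriptive count and listing

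*Combined protocol and SAP*

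**What the plan says.** The link between the C-SSRS and its analysis runs through several sections.

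- **Membership.** The behavioral assessments in 6.3.12 include "Columbia Suicide Severity Rating Scale (C-SSRS" together with the BDI, BAI and PDQ-39. The schedule in 6.1 groups the same four instruments.
- **Analysis.** Sections 9.1.3 and 9.4 give this group one exploratory entry, "Slope of change over 12 weeks of behavioral assessments between placebo and active group", with LMER as the method. Section 9.4 treats the motor stage the same way: "Slope of change over 12 weeks of the Hoehn & Yahr Score".
- **Other summaries.** The only change-score comparison is "Absolute change over 12 weeks of the MDS-UPDRS Parts 1, 2, 3, 4, and TMS", which covers neither measure. No count, listing, responder definition or shift table is planned for either.
- **Timing.** Footnote f to the schedule limits week 2 to the PDQ-39, so on study the C-SSRS falls at Day 1, week 6 and week 12.
- **Adverse events.** Section 10.3.1.1 says that outcome-measure results are collected and analysed separately, and are not recorded as adverse events. Section 9.4 compares adverse events between arms as one overall rate, by chi-square.
- **Entry.** Exclusion 11 in 4.2 uses a yes to Question 4 or 5 "on the suicidal ideation portion of the Columbia-Suicide Severity Rating Scale (C-SSRS") as a case definition. No such definition is used after entry.

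**The concern.** For a suicidality scale, a safety reader needs to know who became positive, when, and on which arm. The protocol itself uses the instrument that way at screening. After randomization the only planned output is a difference between two average rates of change. Falls and orthostatic hypotension, by contrast, are compared in 9.4 as prevalences.

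The exclusion of outcome-measure results from the adverse-event record makes this matter more. For the C-SSRS, the separate analysis promised in 10.3.1.1 is the slope. A team that follows the plan exactly could report a non-significant exploratory slope, and have it read as reassurance, while a positive answer on the form appears in no table.

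The Hoehn & Yahr stage raises a smaller question of the same kind. It is ordinal, with stages I to III eligible under 4.1, and a linear slope treats the stages as equally spaced numbers.

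**Working it through.** The documents give no power, alpha or effect size for these outcomes. Section 9.2 says only that "This is a pilot study and the sample size was chosen based on available funding and resources". There is therefore no figure to reproduce, and the checks below use constructed data.

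**Inputs from the documents.** The arms come from the synopsis: "10 participants will be randomized to receive 5mg of TZ daily and 10 participants will be randomized to the placebo group". C-SSRS times are 0, 6 and 12 weeks; Hoehn & Yahr times are 0, 2, 6 and 12 weeks (6.1).

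**Assumptions.** An ideation score is the modelled variable (the plan defines none). Everyone else scores zero, there is no dropout or measurement noise, visits are on schedule, and tests are two-sided. With complete balanced data, the mixed-model time-by-arm estimate equals the difference in mean per-participant least-squares slopes, so those slopes are used.

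**1. Weight of each C-SSRS visit.** Slope = Σ(t − t̄)y / Σ(t − t̄)². Here t̄ = 6, the deviations are −6, 0 and +6, and the denominator is 36 + 0 + 36 = 72.

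- Score 4 or 5 at week 6 only: 0 × y / 72 = 0. The arm contrast is exactly 0.00.
- Score 4 at week 12 only: 6 × 4 / 72 = 0.333 per week, or 4.0 per 12 weeks for that participant. The arm mean is 4.0 / 10 = 0.40.
- Score 4 at weeks 6 and 12: the same 0.40, because week 6 has no weight.

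**2. Test of that contrast.** With one non-zero slope x among 10, the arm mean is x/10. The variance is (x² − x²/10)/9 = x²/10, so the standard error is √(x²/100) = x/10. The placebo variance is zero. Hence t = 1.0 on 18 df and p = 0.33. A random-intercept fit gave p = 0.22. Random-slope fits on such near-constant data often failed to converge, and their p-values are not used.

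**3. What a count would show.** One case v none is 1/10 = 10% (exact 95% CI 0.3% to 44.5%) v 0/10 (0% to 30.8%). Fisher's p is 1.00 for 1 v 0, 0.47 for 2 v 0, 0.21 for 3 v 0, 0.087 for 4 v 0 and 0.033 for 5 v 0. The gain is in visibility, not in testing.

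**4. How often it would matter.** The chance of at least one case in an arm of 10 is 1 − (1 − r)¹⁰. At assumed rates r of 1%, 5% and 10% this is 9.6%, 40.1% and 65.1%.

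**5. Hoehn & Yahr.** Here t̄ = 5, the deviations are −5, −3, 1 and 7, and the denominator is 84. One TZ participant who worsens by one stage at week 12 gives 12 × 7/84 / 10 = 0.10 stage per 12 weeks. Worsening from week 6 gives 12 × 8/84 / 10 = 0.11. For either, p = 0.33 (random intercept 0.12). One up and one down in the same arm cancel to 0.00. With 2, 3, 4 and 5 TZ participants worsening and none on placebo, the slope test gives p = 0.15, 0.065, 0.025 and 0.008. Fisher on the same counts gives 0.47, 0.21, 0.087 and 0.033.

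**The case against.** **Cases could still reach the adverse-event record.** Section 10.3.1.3 has participants asked about problems or symptoms at every visit and call. A volunteered symptom can be logged, and a serious one must be reported within 24 hours. This stands. A reader might infer that the plan would let no suicidality case surface anywhere; the documents do not support that. The exclusion in 10.3.1.1 covers scale results, not symptoms that a participant reports. What remains is that a case found only on the form has no reporting route, and a volunteered one loses its identity in the pooled rate.

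**A single case is non-significant under any method.** This is also right. Reading p = 0.33 as proof of a wrong model would be a mistake, since the count gives p = 1.00. The evidence against the slope is the zero weight at week 6 and the lack of any participant-level output.

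**Hoehn & Yahr.** A reader might infer that its slope cannot show a stage change. The calculations contradict this: several changes in one direction register, and more readily than Fisher's test on the counts. The measure is exploratory, and replacing its slope would be a matter of preference.

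**The C-SSRS is not named in 9.4.** True; its place there is inferred from 6.1 and 6.3.12. If the behavioral entry were not meant to cover it, the C-SSRS would have no planned analysis at all, so the remedy is the same.

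**Relevance.** The outcome is exploratory, the trial is a pilot, and suicidality is not among the expected terazosin effects in 2.3 and 7. That limits the urgency, but the repair costs almost nothing.

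**Conclusion.** The concern holds for the C-SSRS as a gap in analysis and reporting. As planned, a participant positive only at week 6 changes the slope contrast by 0.00, and one scoring 4 at week 12 appears as 0.40 points per 12 weeks with p = 0.33. Unless the symptom is also volunteered, neither would be reported by arm, although safety and tolerability is the primary outcome.

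The exact zero depends on complete data and visits at the nominal times. A missing week 12 or uneven visit dates would give week 6 some weight, but would still produce no count of cases. The score values and event rates are illustrative, and measurement noise would make the slope p-values larger.

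For Hoehn & Yahr the point is minor. Single changes are diluted and opposite changes cancel, so a table would be a useful addition to the planned slope.

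**What to change.** 1. In 9.4, take the C-SSRS out of the behavioral mixed-model entry. Keep LMER for the BDI, BAI and PDQ-39.
2. Under safety, report by arm the number of participants with any new or worsened ideation or behavior after the first dose, with exact 95% confidence intervals. Add a per-participant listing that gives arm, visit and answers, and includes assessments at early end-of-study visits. Define worsened in the SAP, because only Questions 4 and 5 exclude at entry and lesser positive answers may be present at baseline.
3. Name the pre-dose reference: the screening C-SSRS, or a Day 1 C-SSRS confirmed as done before dosing. Footnote c to the schedule puts Day 1 baseline assessments before randomization, while 6.2.1 allows other assessments during the three hours after the first dose. The two places must be reconciled.
4. Optionally, add a baseline-to-week-12 Hoehn & Yahr shift table by arm beside the planned slope.

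The cost is SAP wording and one or two small tables, with no new data. The count is descriptive and should be presented without a claim of power.

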10 DATA COLLECTION, SITE MONITORING, AND ADVERSE EXPERIENCE REPORTING

10.1 Data Management

Site personnel will collect, transcribe, correct, and transmit the data onto source documents, CRFs, and other forms used to report, track and record clinical research data. The PI will monitor clinical sites to ensure compliance with data management requirements and Good Clinical Practices. The PI is responsible for developing, testing, and managing clinical data management activities.

10.1.1 Data Entry

Data will be entered in RedCap. Data quality assurance and analyses will be performed by the PI.

Data collection for this study will be accomplished with paper forms that will be transcribed into RedCap. The paper forms will be stored in a locked filing cabinet in a locked office, in a badge-access area.

10.2 Role of Data Management

Data Management (DM) is the development, execution and supervision of plans, policies, programs, and practices that control, protect, deliver, and enhance the value of data and information assets.

All data will be managed in compliance with University of Iowa policies, and applicable Sponsor and regulatory requirements.

10.3 Adverse Experience Reporting

The adverse event (AE) definitions and reporting procedures provided in this protocol comply with all applicable United States Food and Drug Administration (FDA) regulations and International Conference on Harmonization (ICH) guidelines. The PI will carefully monitor each subject throughout the study for possible adverse events. All AEs will be documented on CRFs designed specifically for this purpose. It is important to report all AEs, especially those that result in permanent discontinuation of the investigational product being studied, whether serious or non-serious.

Receipt will be kept in the investigator's study file.

An adverse event is defined as: "an unfavorable and unintended sign, symptom, or disease associated with a subject's participation in this research trial."

Serious adverse events include those events that: "result in death; are life-threatening; require inpatient hospitalization or prolongation of existing hospitalization; create persistent or significant disability/incapacity, or a congenital anomaly/birth defects."

Unexpected adverse event is defined as any adverse experience...the specificity or severity of which is not consistent with the risks described in the protocol.

Expected adverse events are those that are known to be associated with or have the potential to arise as a consequence of participation in the study.

On-line Adverse Event Reporting System

Serious adverse events: The site investigator determines causality (definitely not related, probably not related, possibly related, probably related, definitely related) of the adverse event. The PI will prepare a Medwatch safety report for submission to the FDA.

Non-serious adverse events: Non-serious adverse events that are reported to or observed by the investigator or a member of his research team will be submitted to the PI within 24 hours.

10.3.1 Definitions of Adverse Events, Suspected Adverse Drug Reactions & Serious Adverse Events

10.3.1.1 Adverse Event and Suspected Adverse Drug Reactions

An adverse event (AE) is any unfavorable and unintended sign (including a clinically significant abnormal laboratory finding, for example), symptom, or disease temporally associated with a study, use of a drug product or device whether or not considered related to the drug product or device.

Adverse drug reactions (ADR) are all noxious and unintended responses to a medicinal product related to any dose. The phrase "responses to a medicinal product" means that a causal relationship between a medicinal product and an adverse event is at least a reasonable possibility, i.e., the relationship cannot be ruled out. Therefore, a subset of AEs can be classified as suspected ADRs, if there is a causal relationship to the medicinal product.

Examples of adverse events include: new conditions, worsening of pre-existing conditions, clinically significant abnormal physical examination signs (i.e. skin rash, peripheral edema, etc), or clinically significant abnormal test results (i.e. lab values or vital signs), with the exception of outcome measure results, which are not being recorded as adverse events in this trial (they are being collected, but analyzed separately). Stable chronic conditions (i.e., diabetes, arthritis) that are present prior to the start of the study and do not worsen during the

FAST TZ-PD

Version 2.0

Version date: 11/12/2019

trial are NOT considered adverse events. Chronic conditions that occur more frequently (for intermittent conditions) or with greater severity, would be considered as worsened and therefore would be recorded as adverse events.

Adverse events are generally detected in two ways:

Clinical → symptoms reported by the subject or signs detected on examination.

Ancillary Tests → abnormalities of vital signs, laboratory tests, and other diagnostic procedures (other than the outcome measures: the results of which are not being captured as AEs).

If discernible at the time of completing the AE log, a specific disease or syndrome rather than individual associated signs and symptoms should be identified by the Site Investigator and recorded on the AE log. However, if an observed or reported sign, symptom, or clinically significant laboratory anomaly is not considered by the Site Investigator to be a component of a specific disease or syndrome, then it should be recorded as a separate AE on the AE log. Clinically significant laboratory abnormalities, such as those that require intervention, are those that are identified as such by the Site Investigator.

An unexpected adverse event is any adverse event, the specificity or severity of which is not consistent with the current Investigators Brochure or package insert or described in the protocol. An unexpected, suspected adverse drug reaction is any unexpected adverse event that, in the opinion of the Site Investigator or Sponsor, there is a reasonable possibility that the investigational product caused the event.

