2.3 Risk/Benefit Assessment

As mentioned previously, TZ is associated with an increased risk for orthostatic hypotension (OH). This is especially important in the setting of PD where the prevalence of OH is significantly increased compared to healthy controls. Patients with PD are also more susceptible to falls, which could also be exacerbated by the presence of OH. The results from the Truven database outlined above demonstrated that patients with PD who were using TZ did not have significantly increased prevalence of ICD-9 codes related to falls compared to PD patients who were not using TZ. However, this study will directly assess whether or not the use of TZ in PD significantly increases the occurrence of orthostatic hypotension and related events, such as falls. TZ is associated with additional adverse effects, such as peripheral edema, palpitations, nausea, asthenia, dizziness, headache and somnolence. Despite these risks, the potential benefit that TZ may provide is significant given that there are no currently available treatments to slow the progression of PD.

FAST TZ-PD

Version 2.0

Version date: 11/12/2019

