6 CLINICAL AND LABORATORY EVALUATIONS/STUDY PROCEDURES

6.1 Schedule of Activities

Evaluation	Screening (-90 days)	Day 1	2 wks	3 wks	4 wks	5 wks	6 wks	9 wks	12 wks
Written Informed Consent	X								
Inclusion/Exclusion Review	X	X							
Documentation of Disease/Disorder	X	X							
Hoehn & Yahr	X	X	X				X		X
Medical History • Overall Medical History • Medical History of PD	X	X					X		X
Concomitant medication review	X	X	X				X		X
Orthostatics^a	X	X	X				X		X
MDS-UPDRS Motor assessment^b	X	X	X				X		X
Physical examination	X	X					X		X
Randomization^c		X							
Dispense Study Drug^d		X							
Blood Draw		X ^c					X		X
MRI		X ^c							X
Neurological examination	X	X					X		X
Body weight and height	X	X	X				X		X
Vital signs	X	X	X				X		X

Finger Tapping Assessments		X	X				X		X
Behavioral Assessments									

 Columbia Suicide Severity Rating Scale Questionnaire for Compulsive Disorders (C-SSRS) Beck Anxiety Inventory Beck Depression Inventory Parkinson's Disease Questionnaire (PDQ-39) 	X ^e	X	X ^f				X		X
Sleep assessment		X					X		X

 Pittsburgh Sleep Quality Index 									
Recent Falls			X	X	X	X	X	X	X
Cognitive Assessments		X					X		X

 Hopkins Verbal Learning Test (HVLT) Symbol Digit Modalities Test (SDMT) MoCa 									
Auditory/Speech Assessment		X	X				X		X
Pregnancy Test for Women of Child-Bearing potential	X	X	X				X		
Timed Up and Go Assessment		X	X				X		X
Drug Accountability/ Compliance			X	X	X	X	X	X	X
Adverse Event Review			X	X	X	X	X	X	X

a) Participants will lie in the supine position for 5 minutes and have their blood pressure checked. The patient will then sit up for 1 minute and have their blood pressure re-checked. The patient will then stand for 3 minutes and have their blood pressure checked. If the participant has a decrease in the systolic blood pressure by 20 or more mmHg after standing for 3 minutes, or a decline of 10 or more mmHg in the diastolic blood pressure, they will be considered to have orthostatic hypotension.

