9 STATISTICAL CONSIDERATIONS

9.1 Outcomes

9.1.1 Primary Outcome (including definition)

The primary outcome measure will be the safety and tolerability of TZ in the select patient population. This will be assessed by comparing the number of participants in each group that experience drug-related adverse drug events as well as assessing the rate of drop out in each group.

To assess the mean change in systolic and diastolic blood pressures at 6 weeks and 12 weeks between the active and placebo groups.

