9.1.2 Secondary Outcome(s)

- Mean change in systolic and diastolic blood pressure from baseline to 6 weeks and 12 weeks
- Prevalence of falls between placebo and active group
- Prevalence of intolerable side effects between placebo and active group
- Prevalence of study discontinuation between placebo and active group
- Differences in overall compliance between placebo and active group

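### The rule against recording outcome-measure results as adverse events can keep measured orthostatic hypotension out of the primary safety comparison, and sections 9.1.1 and 9.4 count different events

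*Combined protocol and SAP*

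**What the plan says.** **Recording rule.** Section 10.3.1.1 gives clinically significant abnormal test results, with laboratory values and vital signs as examples, as adverse events, "with the exception of outcome measure results, which are not being recorded as adverse events in this trial". It adds that these results are collected but analysed separately. The exclusion is repeated under ancillary tests, a heading that begins with vital-sign abnormalities: "other than the outcome measures: the results of which are not being captured as AEs".

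**What counts as an outcome.** The plan gives no list of outcome measures for this rule. Section 9.1.2 includes "Mean change in systolic and diastolic blood pressure from baseline to 6 weeks and 12 weeks", and section 9.1.1 prints, under the primary outcome, "To assess the mean change in systolic and diastolic blood pressures at 6 weeks and 12 weeks between the active and placebo groups". Section 9.4 gives the prevalence of OH its own chi-square test as a secondary outcome. Section 2.3 promises that "this study will directly assess whether or not the use of TZ in PD significantly increases the occurrence of orthostatic hypotension".

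**How OH is defined.** Footnote a of the Schedule of Activities (section 6.1) uses readings only: a systolic fall of 20 mmHg or more after 3 minutes of standing, "or a decline of 10 or more mmHg in the diastolic blood pressure, they will be considered to have orthostatic hypotension". It requires no symptom.

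**How OH is treated elsewhere.** Section 7 names it first among the expected adverse experiences. Sections 6.2.3 and 8 list it as a reason for stopping study drug. Section 10.3 stresses reporting of AEs that lead to permanent discontinuation.

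**Primary numerator.** Section 9.1.1 compares the number of participants with drug-related events. Section 9.4 assigns a chi-square test to the rate of adverse events between groups, with no relatedness condition and no stated counting unit.

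**The concern.** Safety and tolerability are the primary outcome, and OH is the harm the protocol worries about most. A recording rule that sets outcome-measure results aside falls on the type of data by which OH is detected. Two people applying section 10.3.1.1 in good faith could therefore produce different primary AE counts from the same participants. The primary AE result and the secondary OH result could then disagree because of a recording rule and not because of the drug.

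The numerator adds a second open choice. Section 10.3.1.1 itself treats suspected adverse drug reactions as a subset of AEs, so drug-related events and all events are not the same endpoint. The plan does not say which one is primary, and the choice could be made after the data are seen.

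**Working it through.** **1. Does the exclusion reach OH?** Setting the sections side by side:

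- Section 10.3.1.1: outcome-measure results, including vital-sign abnormalities, are not recorded as AEs.
- Sections 9.1.1, 9.1.2 and 9.4: blood pressure change and OH prevalence are outcomes.
- Section 6.1, footnote a: OH is established by blood pressure readings alone.

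On the plain wording, OH found only by the orthostatic readings is an outcome-measure result and is not recorded as an AE. Sections 7, 6.2.3, 8 and 10.3 point the other way, and no text says which prevails. A participant could stop study drug for OH with no AE recorded.

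**2. Would such a case count as drug-related if it were recorded?** It could. Section 6.3.8 says the orthostatic assessment cannot separate a drug effect from the autonomic failure of PD. In section 10.3.1.3 the Possibly Related category, which is marked as a suspected adverse drug reaction, covers a reaction that could have come from either the product or the clinical state. The call stays with the site investigator, in both arms.

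**3. Size of the effect.** The plan gives no expected AE or OH rate, no alpha and no power, and section 9.2 bases the sample size on funding and resources. There is no stated figure to reproduce. The only input from the documents is n = 10 per arm, so one participant is 1/10 = 10 percentage points of that arm's rate. **All counts below are assumed for illustration.**

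The risk difference is d = p1 - p2, with 1 = TZ and 2 = placebo. The Newcombe 95% interval uses the Wilson limits (l, u) of each proportion:

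- lower = d - sqrt[(p1 - l1)² + (u2 - p2)²]
- upper = d + sqrt[(u1 - p1)² + (p2 - l2)²]

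For 7/10 against 1/10 the Wilson limits are 0.397 to 0.892 and 0.018 to 0.404:

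- lower = 0.60 - sqrt(0.303² + 0.304²) = 0.17
- upper = 0.60 + sqrt(0.192² + 0.082²) = 0.81

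| Assumed situation | TZ | Placebo | Difference, points (95% CI) | Pearson p | Fisher p |
|---|---|---|---|---|---|
| All OH cases recorded | 7/10 | 1/10 | 60 (17 to 81) | 0.006 | 0.020 |
| One TZ case omitted | 6/10 | 1/10 | 50 (8 to 75) | 0.019 | 0.057 |
| One placebo case omitted | 7/10 | 0/10 | 70 (29 to 89) | 0.001 | 0.003 |
| One omitted in each arm | 6/10 | 0/10 | 60 (20 to 83) | 0.003 | 0.011 |

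Each omitted participant is assumed to have no other qualifying AE. The difference falls, rises or stays the same according to the arm in which the omission occurs.

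**4. Size of the numerator mismatch.** In one assumed trial:

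| Numerator | TZ | Placebo | Difference, points (95% CI) | Pearson p | Fisher p |
|---|---|---|---|---|---|
| Drug-related (9.1.1) | 7/10 | 1/10 | 60 (17 to 81) | 0.006 | 0.020 |
| Any AE (9.4) | 9/10 | 7/10 | 20 (-16 to 51) | 0.26 | 0.58 |

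Since section 9 sets no alpha, the p-values are descriptive only.

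**The case against.** The strongest reply is that the exclusion removes readings, not diagnosed conditions. New and worsened conditions are AEs in the same sentence of section 10.3.1.1, and footnote a treats a participant who meets the thresholds as having the condition. The same section also accepts "symptoms reported by the subject or signs detected on examination" and allows for a separate AE entry "if an observed or reported sign, symptom, or clinically significant laboratory anomaly" does not belong to a specific disease or syndrome. A site could log OH by any of these routes. This reading is tenable, and it is why the point is that the rule *can* exclude measured OH, not that it will. But the plan does not choose between the readings, and inclusion in a primary endpoint should not depend on who reads the rule.

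Second, the separation looks deliberate and little is lost: OH has its own test, symptomatic OH can still be recorded as an AE, and a participant stopped for OH may count as a drop-out, the other primary component. This limits the seriousness. It does not settle what the primary AE count contains. Drop-out is also undefined, and sections 6.2.3, 6.2.4 and 8 disagree on follow-up after stopping study drug and need to be reconciled.

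Third, all counts are assumed, and in the four omission examples every interval excludes zero and every Pearson p stays below 0.05. That is correct. The examples show how far the estimate can move, not that a conclusion would reverse. The numerator example was likewise chosen to show that the two definitions can diverge.

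Fourth, section 9.1.1 is headed as the definition, so the entry in 9.4 may only be a short label. That is possible, but 9.4 is where the test is specified, and the two should agree.

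**Conclusion.** The concern holds on both parts and should be fixed; confidence is medium because the first part depends on how an undefined term is read. As written, section 10.3.1.1 can keep OH found only by measurement out of the primary AE comparison, in conflict with the way sections 7, 6.2.3, 8 and 10.3 treat OH. The numerator mismatch between 9.1.1 and 9.4 needs no interpretation of that term.

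The one firm size is 10 percentage points of an arm's rate per omitted participant, provided that participant has no other qualifying AE. The direction of any shift in the difference is not fixed. The contrast of 60 points against 20 points between the two numerators rests entirely on assumed counts. OH is not lost to the trial, because its secondary test remains.

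**What to change.** 1. In section 10.3.1.1, limit the outcome-measure exclusion to efficacy and ATP measures. This also takes falls, another safety outcome, out of its reach. Then add a sentence such as: *Orthostatic hypotension per footnote a of the Schedule of Activities that is new or worsened after the first dose is recorded as an AE, with relatedness judged under 10.3.1.3, and is also analysed as an outcome.*
2. In sections 9.1.1 and 9.4, use one numerator: participants with at least one drug-related AE (Possibly, Probably or Definitely Related in section 10.3.1.3) with onset or worsening after the first dose. Report participants with any AE alongside it.

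This takes a few sentences of protocol text and no new data, because orthostatic readings and AE relatedness are already collected. There are two downsides: AE rates may look higher in both arms, and the same OH readings will feed both the primary AE count and the secondary OH test, which the report should state. No stopping rule or other clinical rule is proposed.
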